	11.8	Protocol Amendments	37
	11.9	Protocol Compliance	38
	11.10	Archives: Retention of Study Records	38
	11.11	Early Termination of the Study	38
	11.12	Reporting Requirements	39
12	Refe	erences	40
13	Арр	endix	41
	13.1	Appendix A: Subject's satisfaction questionnaire	41
	13.2	Appendix B: Global Aesthetic Improvement Scale (GAIS)	42

ABBREVIATIONS AND DEFINITIONS OF TERMS

AE Adverse Event

BMI Body Mass Index

CBC Complete Blood Count

CFR Code of Federal Regulations

CRF Case Report Form

CW Continuous Wave

DoB Date of Birth

EKG Electrocardiography

GCP Good Clinical Practice

FU Follow Up

ICH International Conference on Harmonisation

MC Medical Center

MRI Magnetic Resonance Imaging

NSAIDs Non-Steroidal Anti-Inflammatory Drugs

PI Principal Investigator

SAE Serious Adverse Event

SD Standard Deviation

1 Protocol Synopsis

Protocol Number	ALM-Lipo-002		
Study Title	The Safety and Efficacy of Laser Assisted Liposuction and Facial Autologous Fat Grafting with the LipoLife™ System		
Projected Study Period	Initiation Date: Completion Date: October 2018 Completion Date:		
Study Device	Alma Lasers LipoLife™ system		
Study Sites and Participants	Sanctuary Plastic Surgery Boca Raton FL, U 20 participants	JS and Assaf Harofeh MC, Israel\	
Device Description	The Alma Lasers LipoLife™ system consist of FDA cleared LipoDiode 1470 system (K160952) and LipoFlow system (K171242). The LipoDiode 1470 system is intended for use in dermatology and general surgery procedures and indicated, among other indications, for laser assisted lipolysis. The Alma LipoFlow System is used in the aspiration, harvesting, filtering and transferring of autologous adipose tissue and infiltration for aesthetic body contouring. The LipoLife™ system will be used in this study for laser assisted liposuction and facial fat grafting.		
Study Design and Duration	Multi-center, prospective, open label, single arm study. Following the screening visit, eligible subjects will be enrolled into the study. Each subject will undergo laser assisted liposuction surgery w/wo facial fat grafting (5-20 subjects), using the LipoLife™ system. Pre-surgery evaluation visit will be carried out 1 week prior to the surgery. Follow up visits to evaluate safety and efficacy will take place at 1, 3 and 6 months after the surgery. Study duration from first subject enrollment to the last subject completion is expected to be up to 11 months.		
Study Objectives	 Primary objectives To evaluate the efficacy of Laser Assisted Liposuction procedure with the LipoLife™ system. Secondary objectives To evaluate the efficacy of facial fat grafting procedure using autologous fat harvested with the LipoLife™ system. To evaluate subjects' satisfaction. To evaluate procedure related safety. To evaluate fat vitality of the harvested fat with the LipoLife™ system (optional). 		

Primary endpoint

• Improvement in aesthetic appearance as determined by blinded comparison of before and after 2D or 3D (at the Israeli site)/ 3D (at US site) digital photographs, at 3 months follow up visit compared to baseline.

Secondary endpoint

- Improvement in aesthetic appearance as determined by blinded comparison of before and after 2D or 3D (Israel)/ 3D (US) digital photographs, at 1 and 6 months follow up visits compared to baseline.
- Improvement in facial aesthetic appearance in subjects that had a procedure of facial fat grafting, as determined by blinded comparison of before and after 2D or 3D (Israel)/3D (US) digital photographs at 1, 3 and 6 months follow up visits compared to baseline.
- Reduction in body weight measurement at 1, 3 and 6 months follow up visits compared to baseline.

Reduction in abdominal fat thickness, among five (5) subjects that had a procedure of abdominal liposuction, as assessed by Magnetic Resonance Imaging (MRI) at 3 months follow up visit compared to baseline. This test will be held at the US site.

Increase in facial fat volume, among five (5) subjects that had a procedure of facial fat grafting, as assessed by Magnetic Resonance Imaging (MRI) at 3 months follow up visit compared to baseline. This test will be held at the US site.

- Subject's satisfaction, following liposuction procedure, as evaluated by subject's satisfaction questionnaire (based on 5 point Likert scale) at 1, 3 and 6 months follow up visits.
- Subject's satisfaction, following facial fat grafting procedure, as evaluated by subject's satisfaction questionnaire (based on 5 point Likert scale) at 1, 3 and 6 months follow up visits.
- Safety endpoints will include adverse events (AE's) and serious adverse events
 (SAE's) occurring at any time during the trial or follow-ups.
- Fat vitality, as evaluated by cell viability assessment of 10 samples of the harvested fat (optional).

Study Population

Study Endpoints

Twenty (20) subjects, Ten (10) with excessive fat in the lower abdomen (w/wo flanks) and Ten (10) with excessive fat in the outer thighs (w/wo inner thighs), that are willing to undergo laser assisted liposuction. Five- Twenty (5-20) subjects out of this study group should also be eligible for facial fat grafting.

Five (5) subjects will be recruited at [name] clinic in Sanctuary Plastic Surgery Boca Raton FL, US and will undergo abdominal liposuction and facial fat grafting. The rest fifteen (15) subjects will be recruited at [name] at Assaf Harofeh Medical Center in Israel. Facial fat grafting will be optional in the Israeli site.

Page 8 of 42

Subjects with excessive fat in the lower abdomen w/wo flanks or subjects with excessive fat in the outer thighs w/wo inner thighs that are willing to undergo laser assisted liposuction. **Inclusion Criteria** Estimated fat harvesting of 1-3 liters. Subjects (5-20) eligible for facial fat grafting of at least 5 cc for each cheek. Between 18 and 70 years of age. Provided written Informed Consent. Body Mass Index (BMI) >35. Sever skin laxity. Positive pregnancy test. Current smoker. Presence of known malignancy. Active infection in the treatment area. History of autoimmune disorder (e.g., Systemic Lupus Erythematosus [SLE]). **Exclusion Criteria** History of connective, metabolic or atrophic skin disease. History of keloid scarring. Chronic use (>7 consecutive days) of anticoagulants (such as aspirin) or NSAIDs within 15 days prior to enrollment. Subjects with immune system diseases. Subject unable to follow post treatment instructions. Any other reason that in the opinion of the investigator, prevents the subject from participating in the study or compromise the subject safety.

Introduction

2

The dramatic evolution of contemporary plastic surgery has brought liposuction to become the second-most commonly performed elective aesthetic procedure

performed in the USA 1. In this minimally invasive procedure, excess fat deposits are removed, and either discarded or exploited in subsequent lipo-sculpturing procedures aiming to restore the normal appearance of a range of body regions suffering from surgical, accidental or traumatic tissue loss, or disease- or aging-related cosmetic defects ². Autologous fat tissue has become a popular filling material, particularly in the face and hands ³⁻⁵, largely due to its circumvention of complications associated with allogenic fillers and implants, high and simple accessibility, cost-effectiveness and host-compatibility ^{6,7}. Yet, relatively high resorption rates have been reported, averaging 55% within one year of transplantation, with sample composition, purity and viable adipocyte content flagged as key determinants of implanted fat longevity 8-14

The most commonly used liposuction techniques rely on mechanical, thermal, ultrasonic or hydric forces to harvest the desired sample. Laser-assisted liposuction (LAL) induces temperature elevations that lead to liquefication of the adipose tissue and eventual adipocytolysis, enabling removal of larger volumes of fat than traditional liposuction techniques ¹⁵. In addition, the thermal effect elicits collagen deposition and rearrangement, coagulation of vasculature, skin contraction and reduced laxity. Multiple wavelengths can be used to provide for selective photothermolysis, each providing distinct ratios of penetration and scatter, fat absorption, and tissue tightening. In general, high absorption lasers (1370, 1440 and 1470 nm) generate localized thermal damage, while the lower absorption lasers (980, 1064 and 1320 nm) lead to more diffuse tissue response ¹⁶. Overall, LAL is considered safe and tolerable, and has been associated with a lower touch-up rate and improved precision as compared to conventional liposuctioning techniques ¹⁷.

Alma Surgical's LipoLife integrates a 1470 nm diode laser, emitting light preferentially absorbed by water, rendering it ideal for gentle fat tissue collection, with reduced risk of burning and scarring. In addition, its radially emitting fiber reduces emission intensity and subsequently, the risk of burns and internal scarring. Abdominal fat samples harvested with the LipoLife device were more homogenous, demonstrated higher viable adipocyte counts and contained fewer fibrous and blood contaminants as compared to those collected via mechanical liposuctioning ¹⁸. These virtues are expected to yield more long-lasting clinical outcomes, thereby reducing the need for correction or repeat procedures. When deploying the device for Teimourian grades I- II arm contouring in a single-session laser lipolysis procedure in 45 patients, Leclere and colleagues reported an average 4.7-5.5 cm decrease in arm circumference (p<0.01), with slightly better results for grades IIa and IIb patients. Similarly, the average skin pinch decreased by 0.7 cm for grade I patients and 2.1 cm and 2.9 cm for the grade IIa and IIb patients, respectively. Patient-evaluated pain was minimal, and mean downtime was shorter than one day. Complications included prolonged edema in 11 patients ¹⁹. The same group reported on a 26.6-degrees reduction in cervicomental angle in patients presenting Rohrich type IV aging neck undergoing a single LipoLife treatment session; 2/10 patients requested complementary surgery 6 months following LAL ²⁰. When deployed to address gynecomastia, Trelles et al. (2013) reported no complications, skin burns, edema or areolar congestion. In addition, nipple sensitivity was not compromised. Mean chest and areola diameter reductions 6 months posttreatment, were 11.93 cm and 1.80 cm, respectively (p<0.05). A significant degree of skin retraction was observed among all patients and

The present multi-center, open-label, prospective study aims to assess the safety and efficacy of LipoLife, laser-assisted liposuction of abdominal and outer thigh fat samples, as well as the efficacy of facial autologous fat grafting with the harvested fat tissue. Contouring and volumetric enhancement outcomes will be assessed up to 6 months following the procedure.

patients resumed their normal activities within three days of surgery ²¹.

3 The Investigational Device

3.1 Indication for Use

The Alma Lasers LipoLife[™] system (see Fig.1) consist of FDA cleared LipoDiode 1470 system (K160952) and LipoFlow system (K171242).

Figure 1: Alma Lasers LipoLife[™] system

The LipoDiode 1470 system is intended for use in dermatology and general surgery procedures and indicated, among other indications, for laser assisted lipolysis.

The Alma LipoFlow System is used in the aspiration, harvesting, filtering and transferring of autologous adipose tissue and infiltration for aesthetic body contouring. If the harvested fat is to be re-implanted, the harvested fat is only to be used without any additional manipulation.

The complete operating manual describing the LipoLife $^{\text{TM}}$ system will be attached separately.

3.2 Device description

3.2.1 LipoDiode 1470 system

The Alma LipoDiode 1470 system operates with a wavelength of 1470nm which is absorbed in water and supports laser-Assisted liposuction.

The Alma LipoDiode 1470 system comprised of:

- Alma 1470 diode laser device
- LipoDiode kit, including: 30cm, 25cm and 15cm cannulas (see Fig.2)
- Laser optical fibers- Angel fibers 400μm/600μm
- Footswitch
- Safety eyewear
- Operator's Manual

Livilife

Figure 2: LipoDiode

3.2.2 LipoFlow system

The LipoFlow system provides two modes of operation:

- Peristaltic mode: used for tumescent injection.
- Vacuum mode: used for liposuction and fat transplant procedures.

User can activate only one mode at a time.

The Alma LipoFlow system comprised of:

- LipoFlow system console
- Overflow filter
- Re-usable Canister 2000 ml
- Infiltration kit, including: 15cm and 25cm Infiltration cannulas (see Fig.3)
- LipoFlow kit, including tubes and disposable waste bags
- Fat grafting sterile kit, including: sterile canister and sterile tube (see Fig.4)
- Footswitch
- Operator's Manual

Figure 3: Infiltration Kit

Figure 4: Fat grafting sterile kit

3.2.3 Procedure and parameters

Prior to performing the liposuction procedure, local anaesthesia is administered using the LipoFlow peristaltic mode. Tumescent fluid usage is 150 cc to 500 cc for a $10 \times 10 \text{ cm}^2$ area, while the anticipated total mg/kg dosage of tumescent lidocaine should not exceed 45 mg/kg.

Approximately 20–30 minutes should be allowed to enable an adequate diffusion of the tumescent solution and provide effective vasoconstriction.

Liposuction with the LipoLifeTM system involves simultaneous work of laser and suction. Alma 1470 diode laser is used in Continuous Wave (CW) emission mode, Pulse mode and Repeat mode. Power settings are recommended to be selected as a function of the liposuction area: 10-13W (chin, arms and knees), 13W (abdomen, back), and 15W (thighs, hips and buttocks). The laser energy is conveyed into the fat layer using a 3mm cannula which incorporates a 400 or $600\mu m$ optical single-use fiber. The suction tube is connected directly to the cannula so laser and suction will work simultaneously.

The LipoLifeTM system is designed to be operated only by licensed medical practitioners properly trained in its handling and use. Personnel operating the device must read the operator's manual.

4 Study Objectives

4.1 Primary objective:

To evaluate the efficacy of Laser Assisted Liposuction procedure with the LipoLife TM system.

4.2 Secondary objectives:

- To evaluate the efficacy of facial fat grafting procedure using autologous fat harvested with the LipoLifeTM system.
- To evaluate subjects' satisfaction.
- To evaluate procedure related safety.
- To evaluate fat vitality of the harvested fat with the LipoLifeTM system (optional).

5 Study Design

This is a multi-center, prospective, open label, single arm study.

The study will include 6 visits at the medical center: screening, pre-surgery evaluation visit, laser assisted liposuction surgery w/wo facial fat grafting and 3 follow up visits.

Following the screening visit, eligible subjects will be enrolled into the study. Each subject will undergo laser assisted liposuction surgery w/wo facial fat grafting (5-20 subjects), using the LipoLifeTM system. Pre-surgery evaluation visit will be carried out 1 week prior to the surgery. Follow up visits to evaluate safety and efficacy will take place at 1, 3 and 6 months after the surgery (See Figure 5 for an illustration of the study design).

5.1 Study Endpoints

5.1.1 Primary endpoint

Improvement in aesthetic appearance as determined by blinded comparison of before and after 2D/3D digital photographs, at 3 months follow up visit compared to baseline (2D or 3D at Assaf Harofeh MC, Israel and 3D at Sanctuary Plastic Surgery, US).

5.1.2 Secondary endpoints

 Improvement in aesthetic appearance as determined by blinded comparison of before and after 2D/3D digital photographs, at 1 and 6 months follow up visits

compared to baseline (2D or 3D at Assaf Harofeh MC ,Israel and 3D at Sanctuary Plastic Surgery, US).

[figure not shown]
- Improvement in facial aesthetic appearance in subjects that had a procedure of facial fat grafting, as determined by blinded comparison of before and after 2D/3D digital photographs at 1, 3 and 6 months follow up visits compared to baseline (2D or 3D at Assaf Harofeh MC, Israel and 3D at Sanctuary Plastic Surgery, US).
- Reduction in body weight measurement at 1, 3 and 6 months follow up visits compared to baseline.
- Reduction in abdominal fat thickness, among five (5) subjects that had a procedure
 of abdominal liposuction, as assessed by Magnetic Resonance Imaging (MRI) at 3
 months follow up visit compared to baseline. This test will be held at Sanctuary
 Plastic Surgery, US.
- Increase in facial fat volume, among five (5) subjects that had a procedure of facial fat grafting, as assessed by Magnetic Resonance Imaging (MRI) at 3 months follow up visit compared to baseline. This test will be held at the US site.
- Subject's satisfaction following liposuction procedure, as evaluated by subject's satisfaction questionnaire (based on 5 point Likert scale) at 1, 3 and 6 months follow up visits compared to baseline.
- Subject's satisfaction following facial fat grafting procedure, as evaluated by subject's satisfaction questionnaire (based on 5 point Likert scale) at 1, 3 and 6 months follow up visits.
- Safety endpoints will include adverse events (AE's) and serious adverse events (SAE's) occurring at any time during the trial or follow-ups.
- Fat vitality, as evaluated by cell viability assessment of 10 samples of the harvested fat (optional).

5.2 Study Duration

Duration of subject's participation: Up to 8 months from enrollment to termination.

Study duration for entire study sample: Estimated to be 11 months from the enrollment of the first subject to the termination of the last subject. This is based on an estimate of 3 months for recruitment and up to 8 months subject participation.

Figure 5: Study Design - ALM-Lipo-002

6 Study Population and Subject Selection

[figure not shown]
6.1 Source and sample size

Twenty (20) subjects, Ten (10) with excessive fat in the lower abdomen (w/wo flanks) and Ten (10) with excessive fat in the outer thighs (w/wo inner thighs), that are willing to undergo laser assisted liposuction, will be recruited for the study. Five- Twenty (5-20) subjects out of this study group should also be eligible for facial fat grafting.

Five (5) subjects will be recruited at [name] clinic in Sanctuary Plastic Surgery, US and will undergo abdominal liposuction (w/wo flanks) and facial fat grafting. The rest fifteen (15) subjects will be recruited at [name] plastic surgery department at Assaf Harofeh Medical Center in Israel and will undergo abdominal liposuction (w/wo flanks) or outer thighs (w/wo inner thighs) liposuction. Facial fat grafting will be optional at the Israeli site. (See Figure 6 for subjects' selection and source).

The subjects will be recruited by the investigator from within the investigator's patient population and if needed from the general population by use of an IRB\Helsinki approved advertisement.

Figure 6: Subjects selection and source - ALM-Lipo-002

For fat vitality assessment (optional), ten (10) samples of the harvested fat, from 10 subjects at Assaf Harofeh MC will be collected.

6.2 Eligibility

Each subject will be evaluated by the Investigator to assess his/her suitability for entry into this study according to the following inclusion/exclusion criteria:

6.2.1 Inclusion Criteria

Subjects must meet all of the following inclusion criteria to be entered into the study:

- Subjects with excessive fat in the lower abdomen w/wo flanks, or subjects with excessive fat in the outer thighs w/wo inner thighs that are willing to undergo laser assisted liposuction.
- Estimated fat harvesting of 1-3 liters.
- Subjects (5-20) eligible for facial fat grafting of at least 5 cc for each cheek.
- Between 18 and 70 years of age.
- Provided written Informed Consent.

6.2.2 Exclusion Criteria

Any of the following will exclude the subject from the study:

- Body Mass Index (BMI) >35.
- Sever skin laxity.

- Positive pregnancy test.
- Current smoker.
- Presence of known malignancy.
- Active infection in the treatment area.
- History of autoimmune disorder (e.g., Systemic Lupus Erythematosus [SLE]).
- History of connective, metabolic or atrophic skin disease.
- History of keloid scarring.
- Chronic use (>7 consecutive days) of anticoagulants (such as aspirin) or NSAIDs within 15 days prior to enrollment.
- Subjects with immune system diseases.
- Subject unable to follow post treatment instructions.
- Any other reason that in the opinion of the investigator, prevents the subject from participating in the study or compromise the subject safety.

6.3 Subject Withdrawal and Replacement

The participating subjects may withdraw their consent to participate in the study at any time during the study without prejudice as written in the informed consent form. The reason should be clearly stated in the subjects' medical records. Only the data, collected up to the point of consent withdrawal, will be analysed by the Sponsor.

The investigator may withdraw a subject if, in his clinical judgment, it is in the best interest of the subject or if the subject cannot comply with the protocol or if the subject is unable to adhere to appointments. In the event that a subject drops out of the study or is withdrawn from the study, before the primary end point (3 months FU visit), the Termination CRF form should be completed and the subject should be replaced by the investigator, with the sponsor's approval.

The sites will be required to complete treatment and follow-ups for 20 subjects and therefore should enroll 10% more subjects to account for any subject dropouts or subjects that will be lost to follow-up during the course of at least 6 months. Reasonable effort should be made to contact any subject lost to follow up during the course of the study in order to complete assessments and retrieve any outstanding data. The records of subjects who terminate prior to completing the study will be retained and the reason for termination will be documented. The sponsor must be notified of all withdrawals. Subject that have a complete data for the primary endpoint

FU (3 months follow-up after the surgery) is considered as a subject that completed the study.

7 Study Procedures

See table 1 for a summary of the study procedures.

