7.5 Termination visit

The termination visit occurs in parallel with the last follow up visit (6m FU visit). During this visit the coordinator/investigator will fill the termination CRF.

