11.11 Early Termination of the Study

The study may be terminated prematurely by the principal investigator or his/her designee and the sponsor if:

- The number and/or severity of adverse events justify discontinuation of the study
- New data become available which raise concern about the safety of the study device, so that continuation might cause unacceptable risks to subjects.

In addition, Alma Lasers Ltd. reserves the right to discontinue the trial prior to inclusion of the intended number of participants, but intends only to exercise this right for valid scientific or administrative reasons.

After such a decision, the Investigator must contact all participating subjects, and written notification must be sent to the Reviewing Ethics Committee and relevant Regulatory Authorities.

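### After surgery, withdrawal by the investigator ends only observation, yet the plan names no exit assessment before the 6-month visit and replaces the subject

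*Combined protocol and SAP*

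**What the plan says.** Section 6.3 of the protocol separates withdrawal of consent by the subject from withdrawal by the investigator. The investigator's grounds are the subject's best interest, or "if the subject cannot comply with the protocol or if the subject is unable to adhere to appointments". For any drop-out or withdrawal before the 3-month visit, "the Termination CRF form should be completed and the subject should be replaced by the investigator, with the sponsor's approval".

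The same section contains several protections:
- Retrieval: "Reasonable effort should be made to contact any subject lost to follow up during the course of the study in order to complete assessments".
- Retention: "The records of subjects who terminate prior to completing the study will be retained and the reason for termination will be documented".
- A data cut-off tied to withdrawn consent, not to withdrawal by the investigator: "Only the data, collected up to the point of consent withdrawal, will be analysed by the Sponsor".

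A subject counts as having completed the study on reaching 3 months ("Subject that have a complete data for the primary endpoint").

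Section 7.5 places the end-of-study visit at 6 months: "The termination visit occurs in parallel with the last follow up visit (6m FU visit"). Table 1 has no column for an early exit. On premature stopping of the whole study, section 11.11 says "After such a decision, the Investigator must contact all participating subjects" and requires written notice to the ethics committee and authorities. It mentions no closing assessment.

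**The concern.** In a trial of continuing treatment, withdrawing a subject may end exposure. Here the exposure is one operation at Visit 3. Once it has been done, withdrawal can end only the collection of data. A rule that allows this for poor attendance or compliance, while the subject still consents, gives up outcome data that the trial could have had.

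Two things are at stake. The primary endpoint is a blinded comparison of photographs at 3 months, and a subject withdrawn before then contributes no photograph and is exchanged for someone else. Procedure-related safety is a stated objective, and the first scheduled post-operative adverse event assessment with physical examination is at 1 month. If subjects who leave tend to differ in outcome from those who stay, the reported results are those of the stayers, and no analysis can restore observations that were never made.

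**Working it through.** The plan states no power, effect size or expected response rate, so there is no calculated sample size to reproduce. The check has two parts.

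**1. What is collected, by time of exit (operated subject, consent not withdrawn)**

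| Withdrawn by the investigator | Scheduled post-operative data held | What the text then requires | Not called for |
|---|---|---|---|
| Before 1 month | None | Termination CRF, replacement, reason, notice to sponsor | 1-, 3- and 6-month examination, photographs, weight, questionnaires |
| Between 1 and 3 months | 1 month | As above | 3-month (primary) and 6-month assessments |
| Between 3 and 6 months | 1 and 3 months | Reason and notice to sponsor; the Termination CRF and replacement rule does not apply | 6-month assessments |
| Study stopped under 11.11 | Visits attended so far | Contact with every subject; written notices | No closing assessment named |

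The third row arises because the rule in 6.3 is limited to exits before 3 months, and 7.5 has the Termination CRF filled in at the 6-month visit. In the fourth row, the number or severity of adverse events is one of the grounds for stopping.

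Three other provisions bring in information between visits. The opening of section 9 records adverse events reported from consent to final follow-up. Section 9.2 requires anticipated events to be reported whenever they occur. Section 9.6 requires SAE forms to be updated. None of them produces an after-photograph, a satisfaction form or an examination of the treated area.

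**2. How far the planned allowance could move a result**

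Inputs: 20 subjects to be completed and 10% more to be enrolled (6.3); 95% confidence level (10.1). Assumptions: every subject in the allowance is lost after surgery and before 3 months, all are failures, and 18 of 20 completers are improved. The documents give no expected rate, so 18 is purely illustrative.

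- Enrolment as worded: 20 × 1.10 = 22, so 2 are lost. If the 10% is read as a loss rate instead: 20 / 0.90 = 22.2, rounded up to 23, so 3 are lost.
- Completers only: 18/20 = 90.0% (exact 95% CI 68.3% to 98.8%).
- Two lost, both failures: 18/22 = 81.8% (59.7% to 94.8%), a difference of 90.0 − 81.8 = 8.2 points.
- Three lost, all failures: 18/23 = 78.3% (56.3% to 92.5%), a difference of 90.0 − 78.3 = 11.7 points.

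These are bounds under the stated assumptions, not forecasts.

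**The case against.** The strongest reply is that the protocol is less bare than it looks. The investigator may withdraw a subject but need not, and someone who misses one visit is not clearly unable to attend. The retrieval clause may reach many who fail to appear. Adverse events are reportable outside visits, existing records are kept, and discontinued subjects are listed with reasons (10.2). The study is small, single-arm and descriptive.

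Most of this stands, and it rules out several stronger readings that a reader might infer:

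- **That safety data are lost wholesale.** They are not. Recorded and reported events are kept. The Termination CRF is not reproduced in the documents and may ask for adverse event status.
- **That the complication rate would be shown as 0/20 when it is really 2/22.** Section 10.3 covers all adverse events and does not limit the safety summary to completers. The exclusion mentioned in 10.2 is from the efficacy analysis. Nothing makes 20 the safety denominator.
- **That those withdrawn are the subjects who did worst.** The grounds quoted concern compliance and attendance. A link with outcome is plausible, but the documents do not show one.
- **That a study stop ends follow-up of operated subjects.** Section 11.11 is silent on follow-up. It does require contact with every subject.

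What the reply does not answer is the subject who is withdrawn but reachable. The retrieval clause names those lost to follow-up, not those withdrawn by the investigator, and replacement weakens the reason to pursue them.

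**Conclusion.** The point holds in a limited form. For an operated subject who has not withdrawn consent, section 6.3 permits withdrawal on grounds of compliance or attendance and, before 3 months, attaches to it a form and a replacement but no assessment. The loss is confined to scheduled examination, photographs, weight and questionnaires after the last attended visit. It is total for scheduled post-operative data only if exit comes before 1 month. Exits between 3 and 6 months and a stop under 11.11 share the missing assessment.

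The worst-case effect on a proportion improved is about 8 points with 2 subjects lost and about 12 with 3. This rests on the illustrative 18/20, on all losses being post-operative withdrawals, and on all being failures. The allowance also has to cover exits in the period of up to 2 months between enrolment and surgery, so the actual effect may well be smaller. The change is worth making because it costs little and data not collected cannot be recovered later.

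**What to change.** 1. In 6.3, state that after surgery a missed or late visit is recorded as a protocol deviation and is not by itself a reason to end follow-up, and that the remaining scheduled visits are kept unless consent is withdrawn. Add that such a deviation does not on its own make the subject ineligible for analysis under 11.9.
2. In 6.3 and 11.11, state that if a subject exits at any time before 6 months, or the study is stopped, the already scheduled follow-up assessments (adverse events with physical examination, photographs, weight, questionnaire) are sought at exit, subject to consent.
3. Add early exit as an occasion for the termination visit in 7.5 and Table 1.
4. In 10.3, state that every operated subject stays in the safety summary, whether or not replaced.

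No new procedure is introduced and no treatment rule changes. The cost is protocol wording, some site effort to keep about 2 subjects in follow-up, and a few out-of-window photographs to flag. The documents show no budget, so the financial cost cannot be checked.
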